### 10.1.5 Subject Global Assessment

Subjects will rate their global assessment by answering the following question:

Overall, how would you rate the investigational product you received?

- Poor (0)
- Fair (1)
- Good (2)
- Very Good (3)
- Excellent (4)

## 10.2 Efficacy Assessments/Endpoints

### 10.2.1 Primary Endpoint

The primary endpoint is the sum of the time-weighted pain intensity differences (PIDs) from baseline with movement (SPIDMOVE) over 0-24 hours post-T0 (SPIDMOVE 0-24 hours). Muscle pain/soreness with movement will be scored using the PI-NRS described in [Section 10.1.1](#) at the time points described in [Section 11](#). The PIDs from 0-24 hours after T0 will be calculated by subtracting each post-T0 pain score from the baseline (prior to T0) pain score. The weight given to each PID will be equal to the elapsed time since the previous evaluation.

### 10.2.2 Key Secondary Endpoints:

- SPIDMOVE over the following intervals: 0-6, 6-12, 0-12, 12-24, 24-36, 0-36, 24-48, 36-48, and 0-48 hours post-T0.

### 10.2.3 Other Secondary Endpoints:

- Sum of time-weighted differences from baseline in muscle stiffness with movement (SSIDMOVE) over the following intervals: 0-6, 6-12, 0-12, 12-24, 0-24, 0-36, 24-48, and 0-48 hours post-T0.
- Total relief with movement (TOTPARMOVE) over 0-6 hours post-T0.
- Subject's global assessment of study medication assessed at approximately 48 hours post-T0 (or upon early termination, if applicable).

## 10.3 Safety and Screening Assessments

### 10.3.1 Medical History and Exercise History

A complete medical history will be taken at the Screening Visit. The medical history will include significant past medical or surgical procedures as well as previous and current co-existent diseases. It should include relevant medical history for the following body systems: head, eyes, ears, nose, and throat (HEENT); respiratory; cardiovascular; gastrointestinal; endocrine; hematological; dermatological; genital-urinary (including reproductive history); neurological; musculoskeletal; psychological/psychiatric; and any other history of medical significance. Changes in health occurring between the Screening Visit and the Treatment Period Visit, prior to the first dose of study medication, will be captured as medical history.

At the Screening Visit and Exercise Visit, subjects will be questioned about their exercise history to verify continued eligibility. Subjects who have worked out or exercised the upper extremities with weights or gym equipment during the past 3 months will not be eligible for the study.

### 10.3.2 Adverse Events

Adverse events will be defined, described, recorded, and reported according to [Section 12](#).

### 10.3.3 Local Tolerability Assessments

CBI

CBI

CBI

#### 10.3.4 Clinical Laboratory Tests

The subjects are not required to be in the fasted state for the clinical laboratory testing. Laboratory testing (multiphasic chemistry panel, hematology panel, coagulation, and urinalysis) will be performed at the Screening Visit and on Day 3 at 54 hours post T0. Screening laboratory tests must be reviewed for clinical significance prior to exercise at the Exercise Visit on Day -1 or 2.

[figure not shown]
Urine drug screens and alcohol breath tests will be performed at the Screening Visit, at the Exercise Visit, and on Day 1 prior to the first dose. Urine dipsticks will be used for the urine drug screens.

In women of childbearing potential (WOCBP; women who have experienced menarche and are not postmenopausal or permanently sterilized [by tubal ligation, hysterectomy, or bilateral salpingectomy]), urine pregnancy tests will be performed at the Screening Visit, Exercise Visit and on Day 1 (pre-dose).

CBI

:

[figure not shown]
CBI

**CBI** **Physical Examination**

A complete physical examination will be conducted during the Screening Visit and on Day 3 at 54 hours and will include assessment of the following: HEENT; neck (including an examination of the thyroid); heart; lungs; abdomen (including an examination of the liver and spleen); lymph nodes; extremities; nervous system; and skin.

CBI

A large black rectangular redaction box covers the majority of the page content. The letters "CBI" are printed in red at the top left corner of this redacted area.

An abbreviated, symptom-directed physical examination will be performed at the Exercise Visit on Day -1 or -2. The abbreviated, symptom-directed physical examination is to be performed at the Exercise Visit to re-assess any abnormal clinically significant findings identified at the screening exam and/or to assess any current symptoms at the time of the symptom-directed exam. If there are no abnormal clinically significant findings at the screening visit AND no current symptoms, a symptom-directed examination is not required.

### **10.3.6 Vital Signs**

Vital signs (blood pressure, heart rate, temperature, and respiratory rate) will be recorded at the Screening Visit, at the Exercise Visit (Day -1 or 2), on Day 1 pre-dose, and Day 3 at 54 hours (or at early termination, if applicable). Measurements are to be obtained after the subject has been seated and resting quietly for at least 5 minutes.

Height and weight will be recorded at the Screening Visit.

### **10.3.7 Electrocardiograms**

A 12-lead ECG will be recorded at the Screening Visit and on Day 3 after the subject has been in the supine position resting quietly for 10 minutes. The results must be reviewed for clinically meaningful deviations from normal prior to exercise.

## **11 STUDY PROCEDURES**

An overview of the study assessments and procedures is presented in the Schedule of Assessments, [Appendix 1](#).

### **11.1 Screening Visit (Day -28 to Day -3)**

The investigator or designated qualified study personnel will perform the following assessments at the Screening Visit:

- Obtain written informed consent.
- Verify eligibility via inclusion and exclusion criteria.
- Record demographics.

- Obtain medical history and exercise history. Subjects who have exercised the upper extremities with weights or gym equipment within the prior 3 months will not be eligible for the study.
- Height and weight will be recorded.
- Record prior/current medications and non-medicinal therapies.
- Perform a physical examination, CBI [REDACTED] (as described in [Section 10.3.5](#)).
- Record vital sign measurements (blood pressure, heart rate, temperature, and respiratory rate) after subject has been in a seated position and resting quietly for at least 5 minutes.
- Perform 12-lead ECG with the subject in a supine position after subject has been resting quietly for 10 minutes. Results must be reviewed for clinically meaningful deviations from normal prior to exercise.
- Obtain screening laboratory tests as follows:
  - Obtain blood and urine for screening laboratory tests (multiphasic chemistry, hematology, coagulation, and urinalysis).
  - Obtain urine for urine drug screen.
  - Perform alcohol breath test.
  - Obtain sample for urine pregnancy test for WOCBP.

CBI [REDACTED]

All information and clinical findings will be recorded in the appropriate sections of the CRFs. The investigator will make the final determination of whether a subject is eligible for the study. All subjects screened will be documented on the Screening Log. Specific reasons for excluding any potential subject will be recorded.

## 11.2 Exercise Visit (Day -1 or -2)

Subjects will return to the research unit on the day of exercise. CBI [REDACTED]

CBI [REDACTED]

The following assessments and procedures will be performed prior to the exercise:

- Eligibility will be re-assessed.

[figure not shown]
- Update medical history. Changes in health between the Screening Visit and the Exercise Visit will be captured as medical history.

CBI

A large black rectangular redaction box covering several lines of text.

- Record prior/current medications and non-medicinal therapies.
- An abbreviated, symptom-directed physical examination will be performed, if indicated.
- Vitals signs (blood pressure, heart rate, temperature, and respiratory rate) will be collected after the subject has been seated for at least 5 minutes.
- Obtain urine and perform urine drug screen. Results should be reviewed prior to exercise.
- Obtain urine sample and perform urine pregnancy test in WOCBP. Results should be reviewed prior to exercise.
- Perform the alcohol breath test. Results should be reviewed prior to exercise.

CBI

A very large black rectangular redaction box covering the majority of the lower half of the page.

### 11.3 Treatment Period Visit (Days 1 to 3)

[figure not shown]
CBI

CBI. The following assessments and procedures will be performed to determine eligibility:

[figure not shown]
- Eligibility will be re-assessed.
- Update medical history. Changes in health between the Screening Visit until the Treatment Period Visit, prior to the first dose of study medication, will be captured as medical history.
- Review prior/current medications and non-medicinal therapies.
- Vitals signs (blood pressure, heart rate, temperature, and respiratory rate) will be collected after the subject has been seated for at least 5 minutes.
- Obtain urine for a urine drug screen. Results should be reviewed prior to treatment with IP.
- Perform the alcohol breath test. Results should be reviewed prior to treatment with IP.
- Obtain sample for urine pregnancy test in WOCBP. Results should be reviewed prior to treatment with IP.

CBI

CBI

CBI

- The following assessments are to be completed at CBI [REDACTED], CBI [REDACTED] post first dose of IP and immediately prior to the subsequent doses of IP:
  - Muscle pain/soreness with movement on the PI-NRS
  - Muscle Stiffness with movement on the Muscle Stiffness NRS

- The following assessment is to be completed at [REDACTED] post first dose of IP and immediately prior to a subsequent dose of IP, if one occurs prior to [REDACTED]
  - Relief from starting pain with movement on the Categorical Relief Rating Scale
- [REDACTED].
- At approximately [REDACTED] post-T0, the Subject Global Assessment of IP will be recorded in addition to the [REDACTED] NRS assessments.
- [REDACTED]
- Record any AEs and any concomitant medications or non-medicinal therapies throughout the visit.

On Day 3, at approximately [REDACTED] post-T0, the following assessments and procedures will be performed:

- [REDACTED]
- Perform a physical examination [REDACTED].
- Record vital sign measurements (blood pressure, heart rate, temperature, and respiratory rate) after subject has been in a seated position and resting quietly for at least 5 minutes.
- Perform 12-lead ECG with the subject in a supine position after subject has been resting quietly for 10 minutes.
- Obtain laboratory tests as follows:
  - Obtain blood and urine for laboratory tests (multiphasic chemistry, hematology, coagulation, and urinalysis).
- Any AEs and concomitant medications or non-drug therapies will be recorded.

After these final assessments have been performed, the subject can be discharged from the site.

[REDACTED]

CBI

#### 11.4 Follow-up Telephone Call on Day 7 ( $\pm 1$ day)

Subjects will be called on Day 7 ( $\pm 1$  day) and the following assessments will be performed:

CBI

- Record prior/current medications and non-medicinal therapies.
- Record any AEs.

Each AE will be followed until it resolves, until the investigator assesses the subject's status to have returned to baseline, or until the investigator feels that the event is stable and chronic.

#### 11.5 Order of Procedures

CBI

CBI

## 11.6 Allowable Windows

CBI

## 11.7 Early Termination Assessments

Subjects who discontinue early from the study after receiving IP, will undergo the following assessments and procedures:

CBI

- The subject's global assessment of IP will be recorded (if termination is prior to this 48-hour assessment).
- Perform a physical examination, including a neuromuscular and strength assessment of the upper extremities (as described in [Section 10.3.5](#)).
- Record vital sign measurements (blood pressure, heart rate, temperature, and respiratory rate) after subject has been in a seated position and resting quietly for at least 5 minutes.

- Perform 12-lead ECG with the subject in a supine position after subject has been resting quietly for 10 minutes.
- Obtain laboratory tests as follows:
  - Obtain blood and urine for laboratory tests (multiphasic chemistry, hematology, coagulation, and urinalysis).
- Any AEs and concomitant medications or non-drug therapies will be recorded.

CBI

### 11.8 Subject Withdrawal

If a subject withdraws from the study after the receipt of IP, this will be considered an early withdrawal and the subject should undergo the assessments presented in [Section 11.7](#).

The sponsor should be notified of any withdrawals, and the investigator should record the reason for discontinuation in the CRF. A subject may be removed from the study for medical or administrative reasons such as the following:

- AE
- Lack of efficacy
- Noncompliance with study drug
- Protocol deviation
- Subject withdrawal
- Lost to follow-up
- Physician decision
- Other reasons as determined by the investigator or the sponsor

### 11.9 Estimated Blood Loss

The amount of blood loss during this study per each subject is estimated to be as follows:

CBI

## 12 ADVERSE EVENT REPORTING

### 12.1 Adverse Event Definition

An AE is defined as any untoward medical occurrence in a patient or clinical investigation subject administered a pharmaceutical product and which does not necessarily have to have a causal relationship with this treatment. An AE can therefore be any unfavorable and unintended sign (including an abnormal laboratory finding), symptom, or disease temporally associated with the use of a medicinal (investigational) product, whether or not considered related to the medicinal (investigational) product.

A TEAE is defined as an AE that is new or worsened in severity after the first dose of study drug.

### 12.2 Recording of Adverse Events

The investigator should record any AEs that occur from time of first dose of study medication to 14 days after the last dose of study drug; the investigator should record any SAEs from the time of signing the ICF until 30 days after the last dose of study drug. Adverse events will not be considered treatment-emergent unless they are new or worsened in severity after the first dose of study drug.

At each contact with the subject, the investigator or designee must seek information on AEs by specific questioning and, as appropriate, by examination. All observed or volunteered AEs, regardless of suspected causal relationship to study drug, must be recorded on the AE page of the CRF.

Any events involving illnesses or injuries with onset during the study or any events involving exacerbations of pre-existing illnesses should be recorded. All clearly related signs and symptoms should be grouped together and recorded as a single diagnosis in the CRF. A pre-existing condition must not be reported as an AE unless the condition worsens during the trial. The condition, however, must be reported in the Medical History section of the CRF.

Scheduled or planned diagnostic and therapeutic procedures such as surgery must not be reported as AEs. The scheduled procedure and medical condition for which the procedure was performed must be reported in the CRF.

Each AE will be judged as to the relationship to study medication (as defined in [Section 12.4](#)), the severity (as defined in [Section 12.5](#)), and whether it meets the criteria for an SAE (as defined in [Section 12.6](#)).

Adverse events will be followed until resolution or until the investigator assesses the subject's status to have returned to normal, or until the investigator feels that the event is stable and chronic.

### 12.3 CBI

CBI

### 12.4 Causality Assessments

Each AE will be judged as to whether it is related, possibly related, or unrelated to the IP. The following definitions will be used for these causality assessments.

**Related:** This causal relationship is assigned when the AE:

- starts a reasonable time after study drug administration,
- stops/improves when study drug has been stopped,
- can reasonably be explained by known characteristics of the study drug, and
- cannot be reasonably explained by the subject's clinical state.

**Possibly Related:** This causal relationship is assigned when the AE:

- starts a reasonable time after study drug administration, but
- could have been produced by the subject's clinical state or other modes of therapy administered to the subject.

**Unrelated:** This causal relationship is assigned when the AE:

- is definitely not associated with the study drug administered and is readily explained by other events or diagnoses.

## 12.5 Severity Assessments

The severity of each AE will be graded according to the following definitions:

**Mild:** Does not interfere with subject's usual function.

**Moderate:** Interferes to some extent with subject's usual function.

**Severe:** Interferes significantly with subject's usual function.

## 12.6 Serious Adverse Events

An SAE is defined as any untoward medical occurrence that at any dose:

- Results in death, or
- Is life-threatening,

Note: the term “life-threatening” in the definition of “serious” refers to an event in which the subject was at risk of death at the time of the event; it does not refer to an event which hypothetically might have caused death if it were more severe.

- Requires inpatient hospitalization or prolongation of existing hospitalization,
- Results in persistent or significant disability/incapacity,
- Is a congenital anomaly/birth defect,
- Important medical events that may not result in death, be life-threatening, or require hospitalization may be considered serious when based on appropriate medical judgment, may jeopardize the subject, and may require medical or surgical intervention to prevent one of the outcomes listed in this definition.

Local tolerability findings graded as a 4 using the scoring system in [Section 10.3.3](#) will be considered medically important and reported to the sponsor as SAEs.

All SAEs, from the signing of the ICF until 30 days after the last dose of study drug, must be reported *immediately* (within 24 hours of knowledge of the event) to the Medical Monitor:

PI [REDACTED], MD  
PI [REDACTED]

E-mail: PI [REDACTED]  
Phone: PI [REDACTED]

Reporting via e-mail must be followed up by a follow-up phone call to ensure receipt.

All SAEs must also be reported to the IRB/ Independent Ethics Committee (IEC) per their reporting guidelines. Information regarding the SAE must be completed on the provided SAE report form and recorded in the subject's CRF. The SAE report form and AE page from the subject's CRF should be scanned and emailed to the study personnel named above.

The SAE report forms and instructions will be provided prior to initiation of the study. The SAE report form must be completed with as much information available at the time of reporting. This should, in general, include a description of the SAE in sufficient detail to allow for a complete medical assessment of the case and independent determination of possible causality. New information regarding ongoing SAEs should be provided promptly to the medical monitor. In the case of a subject death, a summary of autopsy findings, if available, should be submitted. The SAE must be reported on the provided SAE report form and the investigator should ensure that the information reported immediately by telephone or other means and in the CRF is accurate and consistent.

The FDA and local regulatory authorities should be notified of AEs that are serious, unexpected, and associated with the use of study drug within 15 calendar days of the sponsor's initial receipt of such reports. The FDA and local regulatory authorities should also be notified of any fatal or life-threatening AEs that are unexpected and associated with use of study drug, within 7 calendar days of the sponsor's initial receipt of such reports. These reports should be submitted in a manner consistent with the applicable local regulatory requirements.

## **12.7 Pregnancy**

If a female subject should become pregnant during the study, the medical monitor must be notified immediately and dosing stopped. Although pregnancy is not considered an SAE, an abnormal outcome of pregnancy may be an SAE. A pregnancy form should be used to report to the sponsor the pregnancy of a female subject. Pregnancies must be followed until birth, termination of the pregnancy, or loss of subject to follow-up.

## **13 DATA HANDLING**

### **13.1 Case Report Forms/Electronic Data Record**

As used in this protocol, the term CRF should be understood to refer to an electronic data record since the data collection method is an electronic data capture system, Medrio eClinical.

A CRF is required and should be completed for each screened subject. The completed original CRFs are the sole property of Aponia Laboratories, Inc. and should not be made available in any form to third parties, except for authorized representatives of Aponia Laboratories, Inc. or appropriate regulatory authorities, without written permission from Aponia Laboratories, Inc.

The investigator has ultimate responsibility for the collection and reporting of all clinical, safety and laboratory data entered on the CRFs and data collection forms (source documents) and ensuring that they are accurate, authentic / original, attributable, complete, consistent, legible, timely (contemporaneous), enduring and available when required. The CRFs must be signed by the investigator to attest that the data contained on the CRFs are true. Any corrections to entries made in the CRFs, source documents must be dated, initialed and explained (if necessary) and should not obscure the original entry.

### 13.2 Clinical Database

Creation and validation of the clinical database and entry and management of data will be conducted in accordance with Title 21 of the Code of Federal Regulations Part 11 and the guidance for industry on computerized systems used in clinical trials. Methods used to ensure the quality and integrity of the data will be documented in the data management plan.

## 14 STATISTICS

Detailed methodology for summary and statistical analyses of the data collected in this study will be documented in a Statistical Analysis Plan, which will be signed off prior to the database lock.

### 14.1 Analysis Populations

The following populations will be utilized:

- **Safety Population:** all subjects who receive at least 1 dose of study drug. The demographic, baseline characteristics, and safety data summaries will be based on the Safety Population.
- **Full Analysis Set (FAS):** all subjects who are randomized, receive at least 1 dose of study drug, and have at least 1 post-baseline efficacy assessment.
- **Per Protocol Set (PPS):** all subjects in the FAS without a major protocol deviation. The sponsor will identify which protocol deviations are considered major before unblinding the study.

## 14.2 Randomization

Study drug will be assigned by predetermined randomization and distributed sequentially starting with the lowest available randomization number. Assignment to active and vehicle control will be in a 1:1 ratio.

## 14.3 Sample Size Determination

A sufficient number of generally healthy subjects of either gender will be enrolled to obtain 250 randomized subjects. The sample size of 250 subjects (125 for each of the treatment group)

CBI

## 14.4 Efficacy Analysis

All statistical testing will be performed with a 2-sided 0.05 level of significance. For each of the time intervals analyzed, completion of administration of the first dose of study drug is considered time 0, T0. Efficacy parameters will be analyzed using both the FAS and the PPS.

### 14.4.1 Primary Efficacy Endpoint and Analysis

The primary efficacy outcome is the sum of the time-weighted differences from baseline in muscle pain/soreness with movement (SPIDMOVE) over 0-24 hours post-T0 (SPIDMOVE 0-24h), that is the area under the differences from baseline pain/soreness intensity difference curve.

The PIDs with movement from time point A to time point B will be calculated using the trapezoid rule by subtracting each post-T0 pain score with movement from the pain score with movement at time point Ti as follows:

- PID with movement at time point i (PIDMOVE i) = NRS score with movement at time point i – NRS score with movement at baseline.
- Mean of adjacent pain intensity differences MMOVE i = (PIDMOVE i + PIDMOVE i+1) / 2
- The weight given to each MMOVE i score (Wi) = elapsed time to the next evaluation (ti+1 – ti).
- SPIDMOVE A-B hr =  $\sum_{i=A}^{B-1} W_i M_{MOVE i}$  where i refers to each NRS scheduled assessment time point between A and B (not including B).

Thus, SPIDMOVE 0-24h =  $\sum_{i=0}^{18} W_i M_{MOVE i}$ , where i refers to each NRS scheduled assessment time point between baseline and 24 hours.

The general formula for computing SPID between any two time points a and b is as follows:

$$SPID_{a-b} = \sum_{i=a}^{b-1} \frac{(t_{i+1} - t_i)(PID_{i+1} + PID_i)}{2}$$

Where i refers to each scheduled assessment time point between a and b hours post baseline,  $t_i$  is the  $i$ th time point and  $PID_i$  is the pain intensity difference at time  $i$

The mean  $SPID_{MOVE}$  for 0-24 hours post- $T_0$  will be compared between the 2 treatment groups using an analysis of covariance (ANCOVA) model with baseline pain/soreness score as a covariate.

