## 8 OVERVIEW OF STUDY DESIGN

This is a Phase 2/3, randomized, single-center, double-blind, vehicle-controlled, parallel-group study designed to determine the efficacy and safety of AP302 (CBI) (CBI) for the treatment of muscle pain/soreness associated with DOMS. Enough subjects will be screened to randomize 250 subjects.

Subjects will be screened up to 28 days prior to the Day 1. After completing the informed consent process, the following procedures will be completed: physical examination, medical history and concomitant medications collection, inclusion/exclusion criteria review, baseline laboratory testing, 12-lead electrocardiogram (ECG), pregnancy testing (females of child-bearing potential), drug and alcohol testing, and vital sign measurements.

Subjects who meet initial inclusion/exclusion criteria will be scheduled to return to the research center to undergo an exercise regimen (CBI)

Between (CBI) hours following the end of the exercise regimen, subjects will return to the clinic to be evaluated for eligibility into the active treatment phase of the study.

To qualify for randomization, subjects must report a (CBI)

CBI

CBI

Qualified subjects will be randomized to receive either AP0302 or vehicle control. CBI

CBI

CBI All doses and efficacy assessments will be completed while the subject is an inpatient at the study site. Subjects will be awakened for IP dosing and efficacy assessments as necessary.

Subjects will complete the following assessments at baseline:

- PI-NRS with movement
- Categorical Pain Rating score with movement (baseline only)
- Muscle Stiffness Numerical Rating Scale (NRS) with movement

The following assessments will be completed at CBI, CBI hours post-initial IP dose and immediately prior to the subsequent doses of IP:

- PI-NRS with movement
- Muscle Stiffness NRS with movement

The following assessment will be completed at CBI post-initial IP dose and immediately prior to a subsequent dose of IP if one occurs prior to CBI:

- Relief from starting pain with movement on the Categorical Relief Rating Scale.

At CBI post-initial dose (or prior to early termination, if applicable), the subject will complete a Subject Global Assessment to give their overall assessment of the IP.

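### Time from end of exercise to T0 can vary between subjects but is not a covariate in the SPID or SSID models: a possible loss of precision, of unknown size, that costs almost nothing to avoid

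*Combined protocol and SAP*

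**What the plan says.** Section 11.2 is headed "Exercise Visit (Day -1 or -2", and the Schedule of Assessments in Appendix 1 allows the same two days. Section 8 adds an interval, with its limits redacted: "hours following the end of the exercise regimen, subjects will return to the clinic to be evaluated for eligibility". The visible text therefore permits the time from exercise to first dose to differ between subjects, but does not show by how much.

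For the primary endpoint, Section 14.4.1 compares mean SPID over 0-24 hours "using an analysis of covariance (ANCOVA) model with baseline pain/soreness score as a covariate"; the synopsis names the same single covariate. Section 14.4.2 applies this model to every other SPID window. In Section 14.4.3 the SSID bullet names baseline muscle stiffness as its covariate.

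On allocation, Section 14.2 states "Assignment to active and vehicle control will be in a 1:1 ratio" and names no stratification factor. Neither exercise day nor time since exercise appears in the visible text as a covariate, a stratification factor or the subject of a sensitivity analysis. Section 14 leaves detailed methods to a later document: they "will be documented in a Statistical Analysis Plan, which will be signed off prior to the database lock".

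**The concern.** The soreness is induced by one scheduled exercise bout, and its onset is delayed by the definition of the condition. SPID is the area under change from baseline after T0, so it contains each subject's natural course as well as any drug effect. The baseline score gives the level of soreness at T0. It does not say whether soreness is still rising or already falling. Two vehicle subjects with the same baseline score, dosed at different times after exercise, can therefore have different expected SPID. The post-exercise entry criterion in Section 8.1.1, whose visible fragment names a moderate rating, narrows the range of baseline scores and so may limit how much timing information they carry.

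If timing predicts SPID after adjustment for baseline pain, that variation stays in the residual error. The standard error of the treatment difference is then larger than it needs to be. At stake is efficiency only; the validity of the test is not in question.

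**Working it through.** **Inputs from the documents.** Section 14.4: "All statistical testing will be performed with a 2-sided 0.05 level of significance". Section 14.3: "The sample size of 250 subjects (125 for each of the treatment group". Allocation is 1:1.

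**Inputs not visible.** The power, effect size, SD and dropout behind the sample size are redacted, so the figure of 250 cannot be reproduced. Design power of 80% or 90% is assumed instead. The association of timing with SPID, given baseline pain, is not stated either; a partial R² from 0 to 0.20 is assumed.

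**Step 1: detectable difference at 125 per arm** (two-sample normal approximation), in residual SD units: d = (z for two-sided 0.05 + z for power) × √(2/125).
- 80% power: (1.960 + 0.842) × 0.1265 = 0.354
- 90% power: (1.960 + 1.282) × 0.1265 = 0.410

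**Step 2: effect of the extra covariate.** The residual variance is multiplied by (1 − R²), where R² is the partial R². Residual degrees of freedom fall from 247 (250 less intercept, treatment and one covariate) to 246, represented by a factor 247/246 = 1.0041. Power = Φ( d / [√((1 − R²) × 247/246) × √(2/125)] − 1.960 ).

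Example at R² = 0.05, from 80%: 0.95 × 1.0041 = 0.9539, with square root 0.9767. Then 0.3544 / (0.9767 × 0.1265) = 2.869, less 1.960 = 0.909, and Φ = 0.818.

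| Partial R² | SE ratio √(1 − R²) | Power, from 0.80 | Power, from 0.90 | Equivalent total N, 250/(1 − R²) |
|---|---|---|---|---|
| 0 | 1.000 | 0.7984 | 0.8988 | 250 |
| 0.01 | 0.995 | 0.8023 | 0.9017 | 252.5 |
| 0.05 | 0.975 | 0.8182 | 0.9129 | 263.2 |
| 0.10 | 0.949 | 0.8382 | 0.9265 | 277.8 |
| 0.20 | 0.894 | 0.8782 | 0.9512 | 312.5 |

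The power columns include the lost degree of freedom; the SE ratio and equivalent N do not.

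**Step 3: what the R² values mean.** For a Day -1/Day -2 indicator with share q, a rough guide is R² ≈ q(1 − q) × (adjusted day difference in SD)².
- 50:50 split: 0.25 × 0.2² = 0.01; 0.25 × 0.3² = 0.0225; 0.25 × 0.5² = 0.0625
- 90:10 split: 0.09 × 0.3² = 0.008
- To reach 0.10 or 0.20 at 50:50, the day difference must be √(0.10/0.25) = 0.63 SD or √(0.20/0.25) = 0.89 SD.

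For day differences up to 0.5 SD, the power gain is thus at most about 2.5 points.

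**Step 4: chance imbalance.** At a 50:50 day split, the between-arm difference in day share has SD √(0.25 × 2/125) = 0.063, about 6 percentage points. It averages zero over randomisations, and the planned standard error already reflects it.

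**The case against.** The strongest reply is that nothing is wrong with the planned model. Under 1:1 randomisation timing is balanced in expectation, the baseline-adjusted test is valid, and the choice of a further prognostic covariate is a design preference. This stands, and it rules out one tempting inference: that chance imbalance in exercise day biases the result.

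A reader might also infer that time since exercise is known to be recorded for everyone and that precision is certainly being given up. The documents support neither. No visible section lists the end time of exercise as a data item. The site must know it to apply the hour window, but that does not establish that it reaches the CRF. A gain requires an association that no visible section reports. The redacted window may be narrow, and baseline pain, measured after exercise, may already carry much of the timing effect. If soreness rises and then falls within the window, a linear term in hours could capture little.

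Calendar day is also a poor stand-in for elapsed time. As an illustration, exercise at 20:00 on Day -2 with T0 at 06:00 on Day 1 is 34 hours, while exercise at 06:00 on Day -1 with T0 at 20:00 on Day 1 is 38 hours. The day order is then the reverse of the time order. This is why day should be only a fallback.

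Finally, a separate SAP is promised, and its text is not available here. It may deal with timing. Even so, both visible statements of the primary model name baseline pain alone, so the matter should be settled before that document is signed.

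**Conclusion.** The point holds as a modest suggestion about efficiency. Timing can vary, the visible models do not use it, and SPID is an outcome that timing could plausibly affect. The planned analysis is valid and unbiased without the change.

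The size cannot be fixed from the documents. On an assumed 80% design power, the change runs from a loss of about 0.2 points if timing is not prognostic to a gain of about 7.8 points at a partial R² of 0.20. From 90%, it runs from a loss of about 0.1 points to a gain of about 5.1. The upper end needs a large timing effect that nothing in the visible text supports, and the gain may be near zero if the hour window is narrow. The case for acting rests on the very small downside, not on a demonstrated loss.

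**What to change.** In Sections 14.4.1 and 14.4.2, and in the SSID analysis in Section 14.4.3, add hours from end of exercise to T0 (as T0 is defined in Section 14.4) as a second prespecified ANCOVA covariate beside the relevant baseline score. State its functional form. Carry the change into the synopsis and the SAP before sign-off, and in any case before unblinding, because a covariate added later would not be credible.

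The sponsor should first confirm that the end time of exercise is captured in the CRF for every subject. If it is not, either add the field or fall back on exercise day (-1 versus -2), derived from visit dates, and acknowledge that it is a cruder proxy.

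The cost is a line of text in each section, one of 247 residual degrees of freedom, and about 0.1 to 0.2 power points if timing turns out not to matter. No new procedure for subjects is needed; a CRF field is needed only if the time is not already captured.
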